5.4 Informed Consent Procedures/Enrollment

5.3a. Aim 1 Vaccine Acceptance Trial. This is a cluster randomized controlled trial design and thus randomization is at the level of VAMC within VISNs 16 and. During the pre-implementation phase (Exempt protocol #E21-06), the study team will meet with leadership of VISNs 16 and 21

and their respective VAMCs to describe the study aims, methods and requirements of each study arm as well as the potential risks/burden and benefits of participation. Specifically, at these meetings, the study team will explain that there is a 50/50 chance that a VAMC will be randomized to be an Intervention or Usual Care site and what is required of each condition. A VAMC assigned to Usual Care will have no specific trial intervention requirements beyond their usual level of participation in national and local initiatives to improve COVID-19 vaccine acceptance. At both Intervention and Usual Care sites, the study team will perform quarterly "environmental scans". The environmental scan survey will include questions about site specific barriers to COVID-19 vaccination, current programs/initiatives in the clinic or local community that are improving or have had no impact on vaccination rates, and the perceived importance that the VAMC/CBOC and clinic staff is placing on vaccination (**Environmental Scan Survey, in preparation**). At Usual Care sites, a point of contact will be chosen from each clinic and CBOC to complete the environmental scan, and at Intervention sites, the Site Champion (**see below**) will perform the quarterly scan.

A VAMC assigned to the Intervention condition will have several requirements. First, VAMC leadership will need to identify and provide release time (about 10% FTE) for a staff member who is already leading the COVID-19 vaccination effort at their site to serve as an Internal Facilitator for their VAMC. The VAMC Internal Facilitator will partner with the trial External Facilitators (research team staff designated as External Facilitators in VISNs 16 and 21) to adapt and implement the study intervention to best meet the needs and preferences of their VAMC site. In addition, each CBOC and clinic affiliated with a VAMC in the Intervention arm will need to identify a Site Champion to provide clinic-specific information to the Internal Facilitator to facilitate implementation of the Vaccine Acceptance Intervention at their clinic or CBOC. In addition, for clinics and CBOCs assigned to the Vaccine Acceptance Intervention, VAMC, clinic and CBOC leadership will need to agree to release PACT staff (who voluntarily agree) for an initial two-hour Motivational Interviewing (MI) training, and at least one 60-minute post-training consultation session over the one-year trial period. There will be additional consultation sessions offered to intervention clinics and CBOC staff, but these will be optional.

All these trial requirements will be explained at the time of the initial meetings with VISN and VAMC leadership in VISNs 16 and 21. At these meetings, in addition to the above information, the study team will answer all questions related to trial participation. The research team will also use these meetings to solicit specific information about VAMC-affiliated clinics and CBOCs to ensure eligibility to participate (primarily based on interest, adequate staffing, adequate release time for staff to participate, and having agreements in place with the VAMC to participate in research). Of note, VAMCs/systems will be able to participate as a study site even if not all VAMC-affiliated primary care clinics and CBOCs are available to participate. Further, all VA staff at participating study sites will be invited but not required to participate in the trial because research is optional and never required. There will be no negative impact for individual VA staff members who opt not to participate in activities related to the trial at an intervention clinic. As a follow-up to the meetings, we will ask the Chief of Staff (or Deputy) or the Medical Center Director (or Deputy) at each VAMC to respond to an email indicating that they agree to have their VAMC participate in the Vaccine Acceptance Study Intervention acknowledging all conditions of participation as explained in the meeting and summarized in the follow-up email. VAMCs will also be invited to have a follow-up meeting with the study team if they have questions or concerns they wish to address prior to considering participation in the study.

Veteran vaccine status and other sociodemographic, clinical, and health service utilization data required to test Aim 1 hypotheses will be obtained through VA administrative databases. We will seek a HIPAA waiver and a waiver of Informed Consent to obtain these data. We will not seek

to obtain data from VA staff who attend meetings or trainings associated with Aim 1 unless they are specifically recruited for qualitative interviews (see Aim 3 below).

Randomization_

This is a cluster randomized parallel group trial design in which the unit of randomization will be at the level of VAMC facility. Cluster randomization is often used to avoid contamination between those receiving the intervention and those who are not. In this case, the Vaccine Acceptance Intervention will occur at Intervention sites and not at Usual Care sites, but we will monitor for evidence of contamination, and if not able to fully guard against it (VA is a national system), we will document examples of potential contamination in the environmental scans described previously.

Randomization will be stratified by VISN (either 16 or 21) and covariate constrained by baseline primary series vaccination rates.⁸¹ Given the likely relatively small number of VAMCs that will be randomized (N \leq 16), we are selecting only one stratification variable (VISN or geographic location) and one or more covariates to constrain on. We have chosen to stratify on VISN given the central importance of location on vaccination outcomes and so as not to have all VAMCs in one VISN randomly assigned to the same study arm. We will also constrain on baseline primary series vaccination rates according to whether sites have lower or higher rates at the start of the study. The number of sites that participate will guide the feasibility of constraining on additional factors, such as rurality, because current data (see **Appendix**, Table 1) suggests that rurality is an important determinant of whether individual patients accept COVID-19 vaccination.

Blinding

The study PIs and co-investigators, other research staff (except for the study statistician, see below), qualitative interviewers and participating VA staff will be unblinded because they are involved in delivering the intervention or, in the case of the qualitative researchers, will be tasked with interviewing study stakeholders about the intervention or implementation strategies. In contrast, the study evaluators, study statistician, and Veterans at VAMC sites in VISN 16 and 21 will be blinded to study arm assignment (Vaccine Acceptance Intervention vs. Usual Care). Thus, evaluators will conduct the study survey in 450 Veterans, and while they will be aware of COVID-19 vaccination status, they will not be apprised of study arm. In addition, unless Veterans are unintentionally informed, Veterans will not know to which arm their VAMC has been randomized. Blinding of the study statistician conducting the outcomes analyses, survey evaluators, and the Veteran participants is important to protect the internal validity of study findings. Despite this being a cluster RCT, outcomes will be ascertained at the patient level.

5.3.b. Aim 2 Veteran Surveys and Interviews

Additional Recruitment Methods: The VA Corporate Data Warehouse (CDW) will be used (via a HIPAA waiver for recruitment) to identify over 8,000 eligible patients over the course of 18 months for inclusion in the cross-sectional survey and qualitative interview across all participating VAMC clinics in VISNs 16 and 21. The following are the broad eligibility criteria used to search VA administrative databases for potentially eligible participants:

- ≥1 visit(s) at a participating VISN 16 or 21 inpatient or outpatient service after the start of the trial at their site.
- Are members of one of two groups with respect to COVID-19 vaccination status:
 - (1) You have either not started COVID-19 vaccination, (2) you received your most current dose of the primary series of a COVID-19 vaccine series after clinicians at your site received the training intervention and within the past 150 days.
- No evidence of dementia using ICD-10 diagnostic codes.

Veteran eligibility data from the VA CDW will be entered into an SQL database by the study team's data manger to which each site's study coordinator will have access. The SFVAHCS will serve as the study's data center. The SFVAHCS has experience in serving as a data center for other NIH- funded (the wHOPE study, [name], PI) and VA HSR&D-funded trials (COACH, [name] PI; [name] site PI). The SFVAHCS study coordinator and data manager will train other study staff involved in recruitment on how to use the database for recruitment and enrollment.

Potentially eligible Veterans (identified through VA administrative databases using a HIPAA waiver for recruitment) will be mailed recruitment materials: patient letters inviting them for a cross-sectional survey and possible qualitative interview, study information sheets, and opt-out postcards addressed to the SFVAHCS data center. We will wait 10 days for opt-out postcards to be returned or for interested patients to call the study staff. If subjects do not opt out or call the study staff first, study staff will contact them via phone; study staff from the Little Rock VA (CAVHS) and staff at the SFVAHCS will contact Veterans in VISN 16 and VISN 21. No cold calls will take place. The recruiter will make up to 5 attempts to reach potential participants and leave up to 3 discrete voicemails. On reaching potential participants, the study staff will attempt to determine interest in participating in the survey, verify COVID-19 vaccination status and assess eligibility using a phone eligibility screener (see Appendix, Draft Phone Eligibility Script/Screener). This screener will assess the following criteria:

o No consistent ability to be contacted by phone

Potential participants who remain eligible after phone screening and interested in participating will be asked if they have email access at home to receive electronic Informed Consent (see below). If so, they will be scheduled for a telephone appointment with study staff at SFVAHCS or at CAVHS for enrollment in the survey study. Eligible patients unsure about participation will be encouraged to discuss study participation with their friends and family and will be provided the option of a future follow-up recruitment call.

Study Enrollment: At the appointed date/time, eligible participants will be recontacted to be enrolled and complete the 60-minute telephone survey. At the beginning of the call, the study coordinator will email the potential participant a link to the electronic Informed Consent (IC) form to be completed via VA-approved DocuSign. DocuSign will require two factor authentication in which the potential participant enters their full name and a working email address to proceed to the IC form. In the case where a participant does not have access to email, the study coordinator will mail out a paper copy of the IC document prior to contacting the potential participant. Regardless of whether the participant receives the IC over email while on the phone or previously via mail, study staff will read through the IC document describing the purpose of the study, the study procedures and the risks and benefits of participating. After each major section of the script, the interviewer will pause and ask whether the participant understood what was read and whether they have any questions. Study staff will use clear, declarative statements when answering these questions. At the conclusion of reviewing sections of the IC, study staff will ask the subject questions to see if they understood basic aspects of the trial as well as relevant human subjects' issues. At the script's conclusion, if the individual is interested in participating, they will be asked to electronically sign the informed consent document or physically sign the copy that was mailed. Study staff will then be able to begin the survey over the phone immediately after obtaining the signed IC document for those using e-consent. For subjects without email/internet, the study staff will have the subject mail back their signed IC document. Once received, a telephone survey will be scheduled.

All study-related contact with potential subjects will be recorded in our SQL database. This includes the Veterans' consent decision and, if they agree to participate, the date and version of the consent document. Potential study participants will be given as much time as they need to consider study participation, limited only by the length of the study period; those wishing to consider study participation further will be invited to call study staff back if and when they are

ready to participate. In these circumstances a later date will be scheduled for completing the survey. We expect the IC process and quantitative survey will take approximately 60 minutes to complete. If the survey becomes a burden at any point during the study, participants will be given the option of completing the interview at another time.

Of note, the IC will request potential participants' consent to possibly re-contact them after the survey to invite them to complete a qualitative interview, if they are needed for the qualitative interview (based on fulfilling purposive sampling targets) and after verifying current vaccine status (recently vaccinated against COVID-19 or persistently declining).

Once the study coordinator verifies the electronic signature on the IC form (via DocuSign) or receives a copy of the signed IC form via mail, participants are considered enrolled in the study and may complete the interviewer-administered survey (see below for details of the survey).

Payments to Study Subjects: We estimate that the IC and survey will take 60 minutes to complete and the qualitative interview could take up to another 60 minutes to complete. To encourage participation and to compensate Veterans for their time and effort, participants will receive compensation after completion of the survey and, if invited, after completing the qualitative interview. Veteran participants will be compensated \$50 for completion of the survey and an additional \$50 when the qualitative interview is complete. The participant will be paid by the VA and the VA requires that subjects receive payment via electronic funds transfer. This requires that the participant fill out their bank information (checking/savings) account number as well as social security number along with a signature on direct deposit forms to return to the VA for processing.

5.3.c. Aim 3: Implementation-Focused Interviews with VISN 16 and 21 Staff

Recruitment Methods: We are planning to conduct mid- and end-of-trial interviews with up to three high and three low vaccination rate clinics per VISN. Mid-trial change in vaccination rate will use the following calculation: 6-month vaccination rate minus baseline vaccination rate. Because of the staggered roll-out study design, mid-trial vaccination rate changes will be calculated at 6-, 7-, and 8-months after the RCT start date. Intervention clinics will be ranked by vaccination rate change from highest to lowest and VA staff and HCPs (e.g., MD, APN, RN, LVN, Pharmacist, Psychologist, Dietician, Social Work, MSA) from these sites will be recruited for qualitative interviews. We expect to interview approximately 3-4 individuals at each site. We will interview individuals who are most familiar with the intervention and/or clinic operations. Site champions and internal and external facilitators will select these individuals to interview from the intervention sites and will provide their names to study staff, who are also VA staff members. For the usual care sites, the point of contact for the environmental scans will provide names to study staff. The study team will email clinic staff and HCPs inviting them to participate in a 1hour phone interview (consent 15 minutes; interview 45 minutes). If the clinic staff or HCPs agree to participate then we will set up an interview time before or after duty hours, on a break, or on leave. Informed consent for staff and HCPs will be verbal and a waiver of documentation of written informed consent will be requested from the Central IRB. Interviews will be audio recorded using a VA-compliant Audacity software.

Study Enrollment: At the appointed date/time, clinic staff and HCPs will be contacted by phone. Study staff will review the information sheet describing the purpose of the interview and research staff will obtain verbal consent to conduct and audio record the interview.

Payments to Study Subjects: We will not be reimbursing HCP and staff participants for their completion of the survey or qualitative interviews.

5.4 Inclusion/Exclusion Criteria (All Study Aims)

Each study Aim has a unique set of inclusion and exclusion criteria summarized below.

5.4. a. Aim 1: Cluster RCT of Vaccine Acceptance Intervention (Randomization at the level of VAMC)

Inclusion criteria:

o Primary care clinic visit in VISN 16 or 21

Exclusion criteria:

o Per VISN or VAMC leadership, the clinic or CBOC has extreme staffing shortages such that it would not be feasible or in the best interests of patient care to allow clinic or CBOC staff release time to participate in trainings or other meetings related to the trial.

5.4.b. Aim 2: Evaluation of recently vaccinated (N=360) and unvaccinated (N=90) Veterans across VISNs 16 and 21 at Intervention and Usual Care sites. *Inclusion criteria:*

- ≥1 visit(s) at a participating VISN 16 or 21 inpatient or outpatient clinic after the start of the trial at their site, and
- At the time of recruitment, COVID-19 vaccination status is verified as one of the following: (1) has not initiated COVID-19 vaccination; (2) has received the most current dose of the primary series of a COVID-19 vaccine after clinicians at their site received the training intervention and within the past 150 days.

Exclusion criteria:

- No consistent ability to be contacted by phone
- Evidence of dementia using ICD-10 diagnostic codes.

5.4.c. Aim 3: Implementation-focused Interviews with VISN 16 and 21 Staff and HCPs

Inclusion criteria: Staff and HCPs work at one of the clinics involved in the study

Exclusion criteria: Staff or HCPs declines invitation to participate in the interview.

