SDR 21-141: Developing and Testing a COVID-19 Vaccination Acceptance Intervention

Multiple PIs: [name] MPH (corresponding), [name], [name]

[Version Number 5.0 Version Date 12.15.23]

Abstract

Background: The COVID-19 pandemic has resulted in significant loss of life with total case and death counts increasing daily. COVID-19 vaccines are effective in preventing symptomatic disease, severe disease, disease transmission, and death. Despite the efficacy and safety of COVID-19 vaccines, many people remain hesitant about vaccination with increased hesitancy among younger individuals (less than 50 years old), Black and Hispanic adults, and those living in rural areas. Recent surveys of Veterans indicate that approximately 35% are unsure whether they will receive a vaccine, highlighting the critical need for evidence-based motivational interventions to increase COVID-19 vaccine acceptance in this population who, without vaccination, remain at risk of severe adverse outcomes and death. The overall objective of this study is to implement and test a COVID-19 vaccine acceptance intervention that is responsive to the needs of Veterans and VA healthcare providers (HCPs) and staff. VA HCPs and PACT staff are consistently identified by patients as trusted sources of vaccine information, thereby best suited to initiate vaccine acceptance discussions with patients. Methods: This evidenceinformed Vaccine Acceptance Intervention will be conducted in VISNs 16 and 21 as a Hybrid Type 2 pragmatic implementation-effectiveness trial, guided by the i-PARiHS framework, and using Implementation Facilitation as the overarching implementation strategy. The specific aims are as follows: Aim 1) Examine the effectiveness of a Vaccine Acceptance Intervention versus Usual Care on Veterans' vaccination rates in a one-year cluster randomized controlled trial. The implementation team will include VISN-level external facilitators, VAMC- level internal facilitators, and clinic-level site champions to support PACT staff and Whole Health Coaches and Peers in implementing the Vaccine Acceptance Intervention with Veterans. Aim 2) Survey Veterans to understand what factors are associated with the decision to accept or not accept COVID vaccination among previously unvaccinated Veterans and through gualitative interviews, learn more about these factors and how they differ between sociodemographically and clinically diverse Veteran subgroups. Aim 3) Learn what aspects of the Vaccine Acceptance Intervention and implementation strategies were helpful and not helpful in improving Veteran vaccine acceptance by conducting mid-trial and end-of-trial gualitative interviews with VISN 16 and 21 study stakeholders using purposive sampling of VA staff and HCPs from sites with high and low vaccination rates. Impact: This is the first multi-site randomized controlled trial to test an MIinformed vaccine acceptance intervention that can be rapidly scaled across VA to improve COVID-19 vaccine acceptance in Veterans. Furthermore, information gained will be used to inform healthcare systems' strategies to improve future vaccination and public health campaigns.

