Because of evolving guidance on COVID vaccinations (products, dosing, etc.) in the context of fluctuating background COVID-19 prevalence at different VAHCS sites combined with seasonal flu vaccination in the Fall and Winter months, we expect temporal and site trends. Therefore, we plan to conduct the following exploratory analyses: (1) adjust for time-dependent variables; and (2) perform analyses stratified by time period and site.

Specific Aim 2 During an 18-month period that overlaps the trial period, we will conduct surveys in a sociodemographically and clinically diverse purposive sample of 450 Veterans equally distributed across VISNs 16 and 21 from Intervention and Usual Care sites with inpatient or outpatient clinic visits (past year) who did (N=360) and did not (N=90) receive COVID-19 vaccination. In addition, in a smaller purposive subset of Veterans (N~90), we will conduct deeper-dive qualitative interviews. These mixed methods will be used to determine correlates and emerging themes related to COVID-19 vaccine acceptance and persistent refusal.

Sample Size Determination: The numbers needed at each stage of recruitment to enroll a total sample of 450 Veterans over 18 months is shown in **Table 4** above. Each month we will enroll 25 Veterans; roughly 20 of whom are vaccinated and 5 of whom are unvaccinated. We will oversample recently vaccinated Veterans to ensure an adequate sample size to be able to describe the impact of the Vaccine Acceptance Intervention on COVID-19 vaccine acceptance after considering other factors. This is primarily a descriptive aim as there is no prior data to guide sample size/power calculations. Our primary hypothesis testing is for Aim 1. For Aim 2, the main research question is whether discussions with VA HCPs and other VA staff impact Veterans' decisions to accept COVID-19 vaccination (and secondarily flu vaccine). For similar reasons, planned sub-group analyses will be primarily descriptive. Given that we anticipate as many as 108,000 to 160,000 unvaccinated Veterans at the start of the trial across VISNs 16 and 21, if we conservatively estimate that 5% will become vaccinated each month (or 5,400-8,000), it is feasible to recruit 25 Veterans each month for a total of 450 over 18 months and ensure that our purposive sampling targets are achieved (**see Table 4 above**).

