1. STUDY SYNOPSIS

Title	The COVID-19 Vaccine Acceptance Study (CoVAcS)		
	The design is a hybrid type 2 (implementation-effectiveness) study. It		
Study Design	consists of a pragmatic cluster randomized controlled 2-arm superiority trial		
	with unit of randomization Veteran Healthcare System (VAHCS) (Aim 1); a		
	survey (Aim 2) and qualitative interviews using purposive sampling (Aim 3).		
Study Duration	3 years		
Trial Sites	VISN 21 and VISN 16 VA facilities		
	Conduct a one-year pragmatic cluster randomized trial to determine the		
	effectiveness of a vaccine acceptance intervention (VAI) training for		
Objectives	healthcare providers and staff in increasing the uptake of any COVID-19		
	vaccination dose in Veterans; conduct a survey to identify predictors of		
	vaccine acceptance/hesitation.		
Number of	10 trial sites in VISNs 16 and 21 (including approximately 90,000 -100,000		
Participants	(Expected); 338,000 (Actual) Veterans		
- articipants	Survey completed: 450 (Expected) Veterans; 224 (Actual) Veterans.		
	Belonging to either VISNs 16 or 21:		
	Aim 1 Trial: Veterans included in the analysis have had one or more primary		
	care visit(s) at a participating VA facility within the past year at the start of		
	site-level randomization.		
Main Inclusion Criteria			
	Aim 2 Survey: Veterans eligible for the trial and who (1) had not started the		
	COVID-19 vaccination and (2) received their most current dose of the		
	primary COVID-19 series in the prior 150 days from when they were		
	contacted and without ICD-10 diagnostic codes indicating dementia and		
	have received primary care at their study site since the study start date at their site.		
	VAI training for health care providers and staff, which includes the use of		
Intervention	Motivational Interviewing to promote vaccine acceptance.		
Duration of	Motivational interviewing to promote vaccine acceptance.		
Intervention and	Intervention (Provider VAI training): 12 months; Follow-up 12-months.		
Follow-up	intervention (Frovider var training). 12 months, ronow-up 12-months.		
·	Study statistician, study evaluators, and Veterans will be blinded to study		
Blinding	arm.		
	Aim 1: Receipt of at least one dose of the COVID-19 vaccine.		
Primary Outcome	74111 1. Necespt of at least one dose of the covid 15 vaccine.		
	All analyses will be according to intent to treat. The difference in proportion		
Primary Analysis	of Veterans receiving any dose at 12 months will be compared between		

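### Aim 2 eligibility does not require the qualifying VA contact to precede the vaccination decision and dates vaccination by the latest primary-series dose, so the vaccinated group can include Veterans who decided before site initiation or before their first post-initiation contact

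*Protocol*

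**What the plan says.** Protocol 5.9 states for Aim 2 that "the main research question is whether discussions with VA HCPs and other VA staff impact" the choice to be vaccinated. The Protocol abstract describes the target as the "decision to accept or not accept COVID vaccination among previously unvaccinated Veterans".

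Protocol 5.4.b (and 5.3.b in near-identical terms) sets two conditions for the vaccinated group:

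- **Visit:** at least one "visit(s) at a participating VISN 16 or 21 inpatient or outpatient clinic after the start of the trial at their site".
- **Dose:** the Veteran "has received the most current dose of the primary series of a COVID-19 vaccine". That dose must fall later than the training of the site's clinicians and be no more than 150 days old at recruitment.

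The SAP synopsis (section 1) limits Aim 2 to Veterans eligible for the trial. It keeps the latest primary-series dose in the 150 days before contact, and requires that respondents "have received primary care at their study site since the study start date at their site". It has no condition that the dose follow training.

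SAP 9.2.1 (Survey Data) calls the design case-control. It models vaccine receipt with a generalized linear mixed model clustered by health care system and mentions no visit, contact or first-dose date.

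**The concern.** A case-control comparison of staff discussions can bear on the decision to vaccinate only if the discussion came before the decision. The criteria leave two gaps.

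- **Order.** The visit and the dose are joined only by 'and'. A Veteran vaccinated at a pharmacy in June whose first post-initiation visit is in August meets the Protocol 5.4.b visit and dose conditions if the site's training came before June.
- **Anchor.** Recency is counted from the latest primary-series dose. A Veteran who accepted the first dose before the site started, and took a later one inside the window, also qualifies.

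The problem is one-sided. An unvaccinated respondent's visit always precedes the status recorded at the survey, whereas a vaccinated respondent's visit need not precede the decision. What is at stake is the reported link between discussion and acceptance, and any contrast in it between the Vaccine Acceptance Intervention (VAI) and Usual Care. Aim 1 is not affected.

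**Working it through.** **1. Every Aim 2 eligibility statement, side by side**

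| Place | Visit | Dose | Visit before dose? |
|---|---|---|---|
| Protocol 5.3.b, 5.4.b | Inpatient or outpatient, after site start | Latest primary-series dose, after training, within 150 days | Not required |
| Protocol 5.3, Aim 2 | Primary care, since site start | Recently received | Not required |
| Protocol 5.9, Aim 2 | Inpatient or outpatient, past year | Did receive | Not required |
| SAP 1 | Trial-eligible, plus primary care since site start | Latest primary-series dose, within 150 days of contact | Not required |

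**2. Latest dose against first dose.** An mRNA primary series has two doses (Protocol 3.0, H1b). For the booster analysis, SAP 9.1.6 also counts a third mRNA dose given less than 60 days after the second as primary series. The latest dose can therefore be one or two doses after the one that marks acceptance.

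**3. What the training condition covers.** It orders the latest dose after training. It does not order the first dose or the visit. Usual Care sites receive no trial training (Protocol 5.3a), so the condition has no defined date there.

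**4. Date check under the SAP wording.** Inputs are the initiation dates in SAP Table 2, the 150-day window, and survey collection from 5/25/2022 to 8/7/2023 (SAP 8.2.1), which is 440 days inclusive. Survey dates stand in for contact dates.

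- Look-back from the first survey day: 5/25/2022 − 150 days = 12/26/2021, before every site's initiation.
- First contact date on which a latest dose before initiation is no longer possible = initiation + 150 days.

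| Sites | Initiation | + 150 days | Survey days before that date | Share of 440 |
|---|---|---|---|---|
| Little Rock, Fayetteville | 02/14/2022 | 07/14/2022 | 50 | 11.4% |
| Las Vegas, Reno | 03/08/2022 | 08/05/2022 | 72 | 16.4% |
| Palo Alto, Northern CA | 03/21/2022 | 08/18/2022 | 85 | 19.3% |
| Honolulu, Fresno | 03/23/2022 | 08/20/2022 | 87 | 19.8% |
| New Orleans, Houston | 04/20/2022 | 09/17/2022 | 115 | 26.1% |

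These are shares of calendar days, not of respondents. After those dates the window alone places the latest dose after initiation, but still does not order the first dose or the visit.

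**5. Illustration of size (assumed inputs).** The documents give no figure for the affected share or for discussion rates. Assume discussion is reported by 50% of correctly ordered vaccinated respondents and 30% of unvaccinated respondents. Let a fraction q of the 139 vaccinated (SAP 6.2.1.2) be misordered and report discussion at rate r. The observed rate among the vaccinated is p = (1 − q) × 0.50 + q × r, and OR = [p/(1 − p)] / [0.30/0.70]. With r = 0.30:

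| q | Respondents of 139 | p | OR |
|---|---|---|---|
| 0 | 0 | 0.50 | 2.33 |
| 0.10 | 14 | 0.48 | 2.15 |
| 0.20 | 28 | 0.46 | 1.99 |
| 0.40 | 56 | 0.42 | 1.69 |

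If visits at or after the dose themselves prompt discussion, so that r exceeds 0.50, the odds ratio moves above 2.33 instead. The direction is not fixed.

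**The case against.** A reader might infer that the vaccinated group does include Veterans whom VA staff cannot have influenced. The documents do not support that, for four reasons.

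- They show whom the criteria admit, not who was enrolled.
- The SAP ties Aim 2 to trial eligibility, which means a primary care visit in the year before the site started. An earlier discussion was therefore possible, and the main question covers discussions with VA staff in general.
- The VAI is not confined to visits. Coaches and Peer Specialists make outreach calls, possibly with priority for Veterans with upcoming appointments (Protocol 5.6.e). Call, then dose, then visit is a plausible intervention pathway.
- Returning for a delayed second dose can itself be a decision, and series completion is the trial's secondary outcome.

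It is also fair to say that Aim 2 is primarily descriptive, that about 90 interviews probe what influenced the decision, and that the survey text was not available, so it may ask when discussions took place. The illustrated odds ratios are well within sampling error. With 139 against 85 and the assumed 50% and 30%, an OR of 2.33 has an approximate 95% interval of 1.3 to 4.1, ignoring clustering.

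These points limit the claim and shape the remedy. They do not supply a rule placing the contact before the decision, and none appears in either document.

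**Conclusion.** The concern holds as a gap in eligibility and analysis. The criteria can admit vaccinated respondents whose first dose preceded site initiation or their first post-initiation contact, and the SAP model does nothing to separate them. The Protocol's training condition is a partial safeguard: it covers the latest dose only, has no date at Usual Care sites, and is absent from the SAP.

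The discussion association and its VAI versus Usual Care contrast may be diluted or reversed in time. Neither size nor direction can be determined from the documents. The odds ratios above rest entirely on assumed inputs, and the date check assumes that contact dates track survey dates. Predictors unrelated to VA contact are little affected, so the finding calls for an added analysis and does not discredit Aim 2 as a whole.

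**What to change.** In SAP 9.2.1 (Survey Data):

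1. Define the decision date as the first primary-series dose, from the Corporate Data Warehouse, or from survey report where the dose was given outside VA.
2. For the discussion and VAI-contrast analyses, add a pre-specified analysis limited to vaccinated respondents whose first dose is on or after site initiation and who had a primary care visit or documented VAI outreach contact between initiation and that dose.
3. Give unvaccinated respondents a comparable index date, for example matched to first-dose dates of vaccinated respondents at the same site, and apply the same contact rule. Otherwise they have longer to accrue contacts.
4. Use the site initiation date as the starting point in both arms. VAI outreach exists in one arm only, so report by arm how many respondents qualify by each route.
5. Report this beside the analysis of all 224.

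Leave the enrolment criteria as they were applied, because survey collection closed on 8/7/2023. State which of the differing Protocol and SAP versions was used for visit type, visit window and the training condition. SAP section 9 allows changes up to data lock and before unblinding; if that point has passed, label the analysis post hoc.

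The cost is fewer than 139 vaccinated respondents in that analysis, wider intervals, the work of linking dates, and some missing dates for doses given outside VA.
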